Study Protocol

Questions raised by the committee – 13-01-2020

1. First, please send us the ethical approval you already received, and second, we need to see the information brochure you are planning to hand to the participants.

Attached to the e-mail I am sending you, you can find the ethical approval we received from METC Zuyderland for the 'larger study' we are going to conduct. Also attached to this e-mail are the information brochures that we are planning to hand to the participants in the **control group** and in the **intervention group**.

As previously explained to you, this larger study supplies the **control sample** for the present study that is under review by the FHML-REC. Therefore, the information brochure for the control group also includes information about measurements that are part of this 'larger study' and that are not for the purpose of the present study. The participants in the intervention group of the present study are waived for the purpose of the present study only, and therefore this information brochure only comprises information about the present study.

2. Please provide us more information about the 'larger study' which has already been conducted, and especially about the intervention and control part of the research

Contrary to what is stated in your question, the 'larger study' has not yet been conducted. Rather, ethical approval for the study has already been waived as can be seen in the attachment to this e-mail. The larger study will be conducted simultaneously with the present study that is currently under review by the FHML-REC (although the duration of the 'larger study' is longer).

Attached to this e-mail is the complete METC application for the larger study, which has already been approved by METC Zuyderland. The summary of this larger study is provided below:

Rationale: From 2015-2020, the 'Healthy Primary School of the Future' intervention took place in Parkstad. The school environment of four primary schools changed. Two schools became 'Healthy Primary Schools of the Future'; providing their students with a healthy lunch and structured physical activity (PA) sessions during lunch time breaks. Two other 'Physical Activity Schools' only implemented the structured PA sessions. METC Z previously decided that this study falls under non-WMO guidelines (METC-Z no. 14-N-142). Interim analyses showed promising effects of the intervention; at two-year-follow-up, the study showed a significant decrease in BMI z-score of children in the 'Healthy Primary Schools of the Future' as compared with children in control schools. Also, positive intervention effects on dietary and PA behaviours were observed. Following these promising results, childcare centres of educational board Prisma have expressed their interest in implementing changes fitting the 'Healthy Primary School of the Future' initiative. However, this is more complex than it seems to be, as budget to implement changes is lower than in the original trial, and all childcare centres have a unique context. Therefore, there is a need to investigate how 'Healthy Primary School of the Future' can successfully be implemented in various, real-life school-settings. It is hypothesised that to maximise implementation and sustainability, each childcare centre will need to put together a set of changes and interventions which fit the context and needs of all stakeholders involved (e.g., the school board, teachers, parents and children).

Objective: The main objective is to study the implementation process of 'Healthy Childcare Centre of the Future' in different school-contexts and develop guidelines that can be used to facilitate widespread dissemination of the initiative. Secondary objectives include evaluating the effects of the 'Healthy Childcare Centre of the Future' on children's BMI z-score, general health, dietary and PA behaviours and school well-being. To reach these objectives, a process evaluation, effect evaluation and cost-effectiveness evaluation will be executed.

Study design: A non-randomised, non-controlled, observational study design.

Study population: Children in study years four to six (at baseline) of twelve childcare centres located in Limburg.

Main parameters/endpoints: The main study parameter of the effect evaluation is the change in absolute BMI z-score, which will be compared between the childcare centres that are categorised based on their degree of implementation (using categories based on the Diffusion of Innovations Theory).

Methods: Data will be collected in the form of questionnaires (parents, children, teachers/pedagogical employees, directors), anthropometric measurements (children), interviews (teachers/pedagogical employees, directors), observations and analyses of minutes of meetings.

Nature and extend of the burden and risks associated with participation: No intervention is allocated in this study other than activities planned by childcare centres in accordance with wishes and needs of childcare centre staff and parents. All outcome measures are non-invasive. The measurement protocol was designed while taking into account both a minimal burden for participants and a relevant scientific

output for stakeholders (e.g., school board, teachers, parents/caregivers and children). Burden of participants is minimalised by incorporating most measurements in the regular school day.

As can be seen from the METC application, this larger study does not include an intervention and a control group, as there is no intervention that will be allocated in this study. Rather, childcare centres can plan their own activities fitting the main idea of the project. The research team will evaluate the implementation process and the effectiveness of these activities.

2.1 It is unclear, why you are asking for the FHML-REC approval only for the intervention part, if you already received one ethical approval previously.

As previously explained, the 'larger study' that will be conducted only delivers the participants of the **control group** of the present study that is under review by the FHML-REC.

To be able to adequately perform the present study, an **intervention sample** needs to be waived, as no such sample is already available in the 'larger study'. Therefore, the intervention group for the present study is not part of this 'larger study'; it is a sample that will specifically be waived for the purpose of the present study that is currently under review by FHML-REC. As the intervention group therefore involves a new sample and an intervention that is not part of the 'larger study', this has not been reviewed by the METC Zuyderland. Therefore, we are currently asking for FHML-REC approval.

Questions raised by the committee – 21-11-2019

- 1. In general, the FHML-REC needs more and better particulars on your study. Therefore, please revise the entire application form and provide more details on the study methodology & design, data processing and data storage, and safeguards to protect the research subjects.**

Study Design

A non-randomised, pre-test post-test controlled trial will be conducted to answer the research questions. The participants in the intervention group will participate in the Learning Street, while the control group receives no intervention and continues with their regular curriculum. None of the participants is subjected to an intervention as part of this study, as children in the intervention group would also have participated in the Learning Street if the present study would not have taken place. The trial is non-randomised, as the intervention group consists of all study years five who participated in the Learning Street for the first time during school year 2019-2020. The school classes included in the control group are chosen from a pool of primary schools already participating in another study and where possible, they are matched to the intervention school classes with regard to potential confounders such as school location and number of students.

Participants and Procedures

Participants are students from study year five (age 8-10 years) of primary schools located in Northern Limburg, the Netherlands. Researchers and employees of Kids University for Cooking will inform children about the study. Information brochures are distributed and parents are asked to give permission for their children to participate in the study. Informed consent will be obtained from all parents of participating children.

Measures and Data Collection Instruments

Measures in the intervention group are performed before the start of the introduction lesson (T0), directly after finishing the evaluation lesson (T1) and three months after the evaluation lesson (T2). In the control group, a similar timing of the measurements will be utilised. At baseline, participants' demographic characteristics (age in years, gender (1=male, 2=female), (parental) birth country (1=western, 2=non-western) are collected via child-reported questionnaire. At all timepoints, children are asked to answer a short questionnaire assessing their psychosocial determinants (knowledge, taste preferences, intention, skills, and attitude) related to the food product that they encountered during their participation in the Learning Street.

Psychosocial Determinants - Questionnaire

Changes in psychosocial determinants of fruit and vegetable intake are selected as outcome measures. Based on the EnRG framework, other literature and the aims of the Learning Street, five relevant determinants are selected: (i) knowledge; (ii) taste preferences; (iii) intention; (iv) skills; and (v) attitude (1–4). Children's knowledge will be assessed by six questions based on what they were taught during the Learning Street.

Three questions are developed regarding the taste preferences (e.g., '*What do you think about the taste of the food product?*') (scale from 1='never tried' to 6='I like it very much'). Questions assessing intention concern participants' plans to consume or cook a meal containing the specific food product in the future and will be assessed on a scale from 1='I don't know' to 6='yes I will'. For skills, children are asked if they are able to cook a meal with the specific food product ('I don't know', 'no', 'a little', 'yes'). Questions and scales for attitude ('*How much do you think the target behaviours are clever/interesting and nice/cool/tasty?*') are used as described by Ajzen and Fishbein and as previously used in comparable research. They are formulated in a way that is simple and understandable for children (scale from 1='no, not at all' to 5='yes, totally') (5,6). The questionnaires were previously used in a pilot study on the Learning Street (7) and appeared appropriate after small adaptations.

Teachers of participating school classes will be visited by Kids University for Cooking BV (intervention group) or researchers (control group) and they will receive a box with envelopes containing the three questionnaires (T0, T1, T2) for every child in their class. For each child, these questionnaires contain a unique ID number (equal for T0-T2 to allow for comparison over time) that cannot be traced back to the child. Teachers write the child's name on the envelope and at each time point, they distribute the right questionnaire to the right child. The questionnaires will be filled out in writing under supervision of the teacher, who will receive written and verbal instructions by researchers and/or employees of Kids University for Cooking regarding the questionnaire procedures. After the questionnaires are filled in, they are collected by the teacher and stored in a separate envelope in the box.

Data Processing and Statistical Analyses

After the T2 measurement, the envelopes with filled-in questionnaires are collected by Kids University for Cooking BV (intervention group) or researchers (control group). The envelopes with the ID number and name of the child, in which the blank questionnaires were stored, are not collected and will remain at the school to be destroyed. This means that only anonymised data will be collected; all non-anonymised data (envelopes with ID number and child's name) will remain at school to be destroyed. Researchers therefore only have access to the anonymised data. All anonymised data will be delivered to the principal researcher at Maastricht University.

In the data analyses, the mean scores of the answers on the questions will be used. Since single unrelated questions will be asked to test different aspects of knowledge, a score of correct answers will be used in further analyses of this determinant.

IBM SPSS Statistics for Windows (version 25, IBM Corp, Armonk, NY, USA) will be used for descriptive analyses. First, the intervention group and control group will be compared on their sociodemographic characteristics by use of Pearson's chi-square tests and independent samples t-tests. Second, mean scores on the various determinants will be calculated. Third, change scores (i.e., the difference in mean score between the baseline measurement and the follow-up measurements) will be calculated. Linear mixed model analyses will be used to assess the longitudinal effect of the intervention on the various determinants assessed in the questionnaire, as this method corrects for correlation within individuals within groups, which occurs in repeated-measures research designs. Another advantage of this technique is that it naturally handles missing values, in case data are missing at random. Since measurements will be repeated within participants, who are nested within classes, we will use a three-level model with classes as third level, participants as second level and measurements as first level. The fixed part of the model consists of group (intervention versus control), time (time-points at which the measurements are taken) and the interaction term group*time. Baseline variables that are related to missing data and/or outcome will also be included to obtain unbiased results and/or to gain precision. As for the random part of the model, a random intercept on class level will be included next to an unstructured covariance structure for the repeated measurements. Relative effect sizes will be calculated for each determinant. These will be expressed as Cohen's d: a Cohen's d of 0.2 is interpreted as a small, 0.5 as a medium and 0.8 as a large effect size (8). Results will be interpreted as significant when $p < 0.05$ (two-sided).

Data Storage

The anonymised data from the questionnaires will be stored and transported in accordance with the Maastricht University Data Management Guidelines (Table 1 and 2). All data will be kept fifteen years after data-collection (GCP) and ten years after publication of the results in a peer-reviewed journal, unless a participant requests otherwise as stated in article 455 book 7 of the Civil law book (in Dutch: Burgerlijk Wetboek).

All data is anonymised using ID numbers so it is impossible to be traced back to a specific participant. Researchers involved in study will only have access to the anonymised research data; no personal data is available to any of the researchers.

Table 1: Storage Locations and Back-Up

	Non-digital data (e.g., paper)	Digital data	Back-up
Non-sensitive data	No restrictions	No restrictions	Network discs
Sensitive, anonymised data	Locked closet in a locked room	Only on network discs. When the file size is too large to store on network discs, an alternative and safe storage location will be chosen after consultation of the principal investigator.	Network discs
Sensitive, anonymised data with ID	Locked closet in a locked room	Only on network discs. When the file size is too large to store on network discs, an alternative and safe storage location will be chosen after consultation of the principal investigator.	Network discs

Table 2: Storage Mediums and Transport

	Email	Encrypted transport on mobile device	Cloud and FTP
Non-sensitive data	No restrictions	No restrictions	Only in cloud and FTP services offered and approved by ICTS
Sensitive anonymised data	No restrictions	No restrictions	Only in cloud and FTP services offered and approved by ICTS
Sensitive anonymised data with ID	Permitted when data is encrypted*	Permitted when data is encrypted* and only when strictly necessary	Only in cloud and FTP services offered and approved by ICTS

* Encryption is done via a difficult to hack password. This contains of at least twelve characters in a non-logical order. The password is not used for other purposes. When a password needs to be shared with another person, this can only be done via separate communication channel.

Safeguards to Protect Research Participants

Data will only be collected if parents of the child have signed the informed consent form provided by researchers. Subjects can withdraw from the study at any time for any reason if they wish to do so without any consequences. This is clearly stated in the information brochure and informed consent form. As the non-anonymised data (envelopes with ID numbers and child's name) will remain at the school, researchers only have access to anonymised data and therefore participants' privacy is safeguarded. Participants are not identifiable in any publications or other dissemination of research results.

1.1 The panel was especially concerned about the data ownership. This aspect was relatively vague in your application and thus, we would like you to clarify this point.

As only anonymised data are used in the present study, the GDPR does not require the draft of a Data Transfer Agreement or any comparable agreement between Maastricht University and Kids University for Cooking. After consulting the GDPR expert of Maastricht University, this agreement is therefore removed from the Appendix of the current application. All anonymised data is property of Maastricht University. The non-anonymised data (envelopes containing ID number and child's name) are property of the school and will not be collected as part of this study. They will remain at the school to be destroyed.

2. Moreover, the panel was wondering if the application was only considering the intervention group. However, in order to make an informed and well-grounded decision, we need to see the entire study.

The procedures considering the control group are comparable to the procedures considering the intervention group (as described in the application). The participants in the control group (children from study year five of various primary schools) are asked to answer the same questionnaires at the same three time points as the participants in the intervention group. However, the control group does not participate in the 'Learning Street', but will continue with their regular curriculum.

School classes in the control group will be waived from a pool of primary schools already participating in a larger study. This larger study examines the implementation process of various health-promoting initiatives at primary schools. As this study is a process evaluation, no intervention is imposed but the implementation process is followed. Schools participating in this research are free to choose if, when and how they want to implement health-promoting initiatives in their school context. Some schools participating in this research are not planning to implement any health-promoting initiatives any time soon. Therefore, these schools can serve as control schools in the present study, as they will continue with their regular curriculum for the duration of the present study. In these control schools, children from study year five and their parents will be informed about the larger study, including the measurements that will be used for the present study. Subsequently, they are asked to give their consent for their child to participate in the study. The information brochure for the control group is not included in this application. This is because this information brochure contains not only information about the procedures of the current study, but also about measurements and procedures related to the larger study, which are not relevant for the current study. If desired, this information brochure can be provided.

Ethics Review of niet-WMO-plichtig research with human participants

Please complete the following in a free style with a high level of detail. The ethics review process is looking to see that you have identified ethical issues and addressed them satisfactorily; further, that you are thinking about undertaking your research in an ethical manner, and can communicate this to your research participants and other people in society generally.

Please attach as an appendix any additional materials to support the application, particularly any information sheets and informed consent forms where relevant.

Return the completed form to:
[contact]

Investigator Name: [name]
E-mail: [contact]

Project Title: Kokkerelli Learning Street Effect Evaluation

Table of Contents

Study Protocol.....	8
1. The Study.....	8
2. Identifying Harms	13
3. Safeguards	14
4. Self-evaluation.....	17
References	17
Appendix I. Information Brochure for Parents (Intervention Group).....	19

Study Protocol

1. The Study

1.1 What is the nature of the study? What are the key questions that you are seeking to address?

In 2012, the Kids University for Cooking Foundation BV has developed a nutrition education programme called 'Kokkerelli Learning Street'. This innovative programme aims to teach primary school students aged 8-12 years (study years 5-8) where food comes from, how it is processed, and how it can be used for the preparation of a healthy meal (1). The theoretical foundation of the Learning Street is based on the EnRG framework, which states that behaviour is influenced both by conscious and unconscious processes. These processes can (in)directly be influenced by environmental factors. In addition, several behavioural and personal factors are thought to moderate the causal path (2). An adapted EnRG framework with important influential factors on fruit and vegetable intake in children can be found in Figure 1.

[figure not shown]

Figure 1. Overview of influential factors on fruit and vegetable intake in children

The Kokkerelli Learning Street is offered to primary school children in the region of Venlo, the Netherlands. It involves education based on concepts of the Self-Determination Theory, active learning, and imagineering (e.g., self-experience in an interactive environment, rather than conventional education) (1,3-5). The present study will investigate the effects of the Kokkerelli Learning Street on several determinants of children's fruit and vegetable intake. Based on the EnRG framework, other literature and the aims of the Learning Street, five relevant determinants are selected: (i) knowledge; (ii) taste preferences; (iii) intention; (iv) skills; and (v) attitude (1,2,6,7). The key questions which the present study will aim to answer are:

What are the short-term and longer-term effects of the Kokkerelli Learning Street on children's:

- Knowledge regarding fruit and vegetable consumption?
- Intentions regarding fruit and vegetable consumption?
- Attitude regarding fruit and vegetable consumption?
- Liking of fruit and vegetables?
- Skills regarding fruit and vegetable preparation?
- Fruit and vegetable intake?

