After the T2 measurement, the envelopes with filled-in questionnaires are collected by Kids University for Cooking BV (intervention group) or researchers (control group). The envelopes with the ID number and name of the child, in which the blank questionnaires were stored, are not collected and will remain at the school. This means that only anonymised data will be collected, all non-anonymised data (envelopes with ID number and child's name) will remain at school. Researchers therefore only have access to the anonymised data. All anonymised data will be delivered to the principal researcher at Maastricht University.

In the data analyses, the mean scores of the answers on the questions will be used. Since single unrelated questions will be asked to test different aspects of knowledge, a score of correct answers will be used in further analyses of this determinant.

Data will quantitatively be analysed using IBM SPSS Statistics for Windows (version 25, IBM Corp, Armonk, NY, USA). Numerical variables will be presented as mean \pm standard deviation (SD), where number (%) will be used for categorical variables. A two-tailed test is considered statistically significant with p-values ≤ 0.05 . Questionnaire items for the determinants knowledge, intention, attitude, skills and taste preferences are combined into one variable per determinant for each time point. Differences in numerical baseline parameters between the control and intervention group will be tested with the independent-samples t-test or Mann-Whitney U-test where appropriate, while the Chi-square test, or Fisher's exact test, will be used for categorical variables. To investigate the in-

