In intervention classes, the data used in this study is collected as part of the Kokkerelli Learning Street. As only anonymised data will be used in the present study, the GDPR does not require the draft of a data transfer agreement or any other comparable agreement between Maastricht University and Kids University for Cooking BV.

In control classes, data is collected as part of another, larger study that will take place at the same time (further specified in an earlier section of this application). Ethical approval for this larger, ongoing study is under assessment by the Zuyderland Medical Ethics Committee. For both the intervention and control group, only data of participants whose parents/caregivers have given informed consent will be used in the present study. All anonymised data will be property of Maastricht University. The non-anonymised data (envelopes with ID number and child's name) are property of the school and will therefore remain at school after data collection to be destroyed.

1.5 What sort of people will be involved? (For example, professionals in the course of their profession, members of the general public.)

Participants will be children aged 8-10 years old (study years five) from primary schools in Limburg, the Netherlands. Parents of these children will be informed by Kids University for Cooking BV (intervention group) or researchers from Maastricht University (control group) about the study. They will receive an information brochure about the study and are asked to give written consent for their child's participation in the study.

1.6 On what grounds did you determine the number of participants needed for the study?

As one of the primary aims of the Kokkerelli Learning Street is to improve children's knowledge with regard to fruit and vegetables, it is expected that the Kokkerelli Learning Street will have positive effects on participants' knowledge. Therefore, the sample size calculation was based on the primary outcome, i.e. to detect a difference in knowledge score between the intervention classes and the control classes three months after the intervention. Unfortunately, limited evidence is available regarding the effects of the Kokkerelli Learning Street or comparable programmes on

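### The primary outcome named for the sample size (knowledge at three months) is not carried into the analysis sections, so no stated test carries the effectiveness conclusion

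*Combined protocol and SAP*

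**What the plan says.** **Primary outcome.** Section 1.6 says that "the sample size calculation was based on the primary outcome, i.e. to detect a difference in knowledge score" between intervention and control classes three months after the intervention. No other section mentions a primary outcome for this study.

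**Outcomes and time points.** Section 1.1 and the reply to the committee of 21-11-2019 both state that "five relevant determinants are selected: (i) knowledge; (ii) taste preferences; (iii) intention; (iv) skills; and (v) attitude". Follow-up is "directly after finishing the evaluation lesson (T1) and three months after the evaluation lesson (T2"). The key questions in section 1.1 begin "What are the short-term and longer-term effects of the Kokkerelli Learning Street on children's" and then list six items in no order of importance. The sixth is "fruit and vegetable intake", which is not among the five determinants.

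**Model.** Both analysis sections specify the same mixed model for the determinants: "The fixed part of the model consists of group (intervention versus control), time (time-points at which the measurements are taken) and the interaction term group*time". Both also promise a Cohen's d for each determinant.

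**Significance rule.** The reply says "Results will be interpreted as significant when $p < 0.05$ (two-sided"). Section 1.2 says "A two-tailed test is considered statistically significant with p-values" at or below 0.05. Neither section names a primary outcome, a primary time point, an order of testing, a multiplicity adjustment, or a class of exploratory results.

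**The concern.** The plan makes a choice in section 1.6 and does not use it where results are declared significant. An analyst could follow either analysis section to the letter, find nothing for knowledge at T2, and report attitude at T1 as a significant effect of the programme. Nothing in the text would mark that result as secondary.

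This matters because of the purpose given in section 1.7. The programme owner wants the Learning Street entered in the Dutch database for effective interventions, and the study is to supply the evaluation of effectiveness needed for that. A reader of the report should be able to tell in advance which test carries that conclusion and at what error rate.

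**Working it through.** **1. The plan's own figure.** Inputs from section 1.6: 7 classes of 25 per group, 10% dropout, ICC 0.04, SD 0.24, alpha 0.05, power 80%. The two-sided test comes from the analysis sections.

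- Analysed per class: 25 × 0.9 = 22.5; per group: 7 × 22.5 = 157.5.
- Design effect: 1 + (22.5 − 1) × 0.04 = 1.86.
- Detectable difference: SD × (z₀.₉₇₅ + z₀.₈₀) × √(2 × DE / n) = 0.24 × (1.960 + 0.842) × √(2 × 1.86 / 157.5) = 0.103. With a t distribution it is 0.104.

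The stated 0.104 reproduces. It is the detectable difference for one test, knowledge at T2, at the full 0.05.

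**2. Number of tests.** Five determinants at two follow-ups give 5 × 2 = 10 contrasts. This count is inferred. The text does not say whether group-by-time is tested separately at T1 and T2 or once per determinant, which would give 5 tests.

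**3. Independent tests.** If all k null hypotheses are true, the chance of at least one p below 0.05 is 1 − 0.95^k.

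- k = 5: 1 − 0.95⁵ = 22.6%
- k = 10: 1 − 0.95¹⁰ = 40.1%

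**4. Correlated tests.** The documents give no correlations, so a range is assumed. Multivariate normal test statistics were simulated (400,000 draws per cell). The correlation between two contrasts was taken as the between-determinant value times the T1-T2 value. The entries give the chance of at least one significant result among ten contrasts, with all nulls true (the cell with both correlations 0 is the exact value):

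| T1-T2 correlation | Between determinants 0 | 0.2 | 0.5 | 0.7 |
|---|---|---|---|---|
| 0 | 40.1% | 38.7% | 33.2% | 27.5% |
| 0.5 | 37.9% | 36.5% | 31.0% | 25.7% |
| 0.7 | 35.4% | 34.2% | 28.9% | 23.7% |
| 0.9 | 30.5% | 29.5% | 24.7% | 20.0% |

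Moderate correlation (0.2-0.5 between determinants, 0.5-0.7 between time points) gives 29-37%. Strong correlation (0.7 between determinants, 0.7-0.9 between time points) gives 20-24%.

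With one overall two-degree-of-freedom group-by-time test per determinant, the rate is 22.6% if independent, 21.9% at correlation 0.2, 18.6% at 0.5 and 15.3% at 0.7.

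**5. Intake as a sixth outcome.** Twelve contrasts would give 1 − 0.95¹² = 46.0% if independent, and 32-42% at the same moderate correlations. This applies only if intake is analysed. It is a key question and appears in the baseline questionnaire described in Table 1 of section 1.2, but not in the list of determinants for analysis.

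**6. Cost of two remedies.** Making knowledge at T2 the only confirmatory test leaves alpha at 0.05 and the detectable difference at 0.104. A Bonferroni correction over all ten contrasts (0.05/10 = 0.005) would raise it to 0.24 × (2.807 + 0.842) × √(2 × 1.86 / 157.5) = 0.135.

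**The case against.** The strongest reply is that the plan does rank its outcomes. Section 1.6 names one primary outcome, fixes its time point, explains why knowledge comes first, and attaches alpha and power to it. Reading everything else as secondary is a common convention, and under that reading the primary test has a 5% error rate. This stands as far as it goes: the primary test is valid. It does not close the gap, because the rules for calling a result significant never refer to section 1.6, and section 1.6 itself calls knowledge only one of the programme's primary aims.

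Three stronger readings are tempting, and the documents do not support them.

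- A reader might infer that any single p below 0.05 makes the study positive. No section defines study success. The two rules say only when an individual result is called significant, and effect sizes are promised alongside.
- A reader might take 40% as the error rate of the plan. It is the upper end for ten contrasts: it needs independence, separate tests at T1 and T2, and no effect on any determinant. Section 1.6 expects an effect on knowledge.
- A reader might infer that one significant determinant would be offered as proof for the database. Section 1.7 says only that a good evaluation is needed, and the database's criteria are not in the documents.

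**Conclusion.** The concern holds as a gap in the analysis sections, not as a fault in the primary test. The plan names knowledge at T2 as primary for the sample size but never ties the effectiveness conclusion to it, while one 0.05 rule covers every determinant.

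If every null hypothesis is true, at least one significant result is expected in about 20-40% of such studies with ten contrasts. With five overall tests the figure is about 19-23% at correlations up to 0.5, and 15% at 0.7. All these figures rest on an assumed test count and assumed correlations. Even the smallest is about three times the nominal 5%, so the need for a stated hierarchy does not depend on which assumption is right. The correction is worth making because it is cheap and uses the sponsor's own choice.

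**What to change.** Add to the analysis section:

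1. The group-by-time contrast for knowledge at T2 (against T0) is the single confirmatory test, at two-sided 0.05, and the effectiveness conclusion rests on it.
2. All other contrasts are secondary or exploratory. Formal secondary claims are made only if the primary test succeeds, with a Holm correction over a named family. An example is the other four determinants at T2, with first step 0.05/4 = 0.0125.
3. T1 contrasts are reported as estimates with 95% confidence intervals and called exploratory. If formal short-term claims are wanted, the five T1 contrasts join the Holm family: 4 + 5 = 9 members, first step 0.05/9 = 0.0056.
4. If intake is analysed, its place in this order is stated.

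Making secondary claims conditional on the primary result is what holds the overall rate at 5%. Without that condition, the primary test at 0.05 plus Holm over four secondary tests would give 1 − 0.95 × (1 − 0.0125)⁴ = 9.7% if independent.

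**Cost.** A few sentences. Secondary claims need smaller p-values and depend on the primary result. The short-term half of each key question becomes exploratory or faces a stricter threshold, which is a real loss given the stated aims. The primary test, the sample size and the detectable difference of 0.104 are unchanged.
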